6.3.4 Maintenance Period

The first Maintenance Visit will occur 2 weeks after the start of dosing at 300 mg/d; thereafter, Maintenance Visits will occur approximately every 4 weeks.

Subjects should withhold their daily home dose of IP on in-clinic dosing days, but should take all other prescribed medications as scheduled.

The following assessments/procedures are scheduled for each in-clinic dosing Maintenance Visit in the CRC:

- Concomitant medication review
- Contraception review
- Diet (food allergen exposure) history update
- Return unused IP to the clinic at each visit
- Symptom-directed physical examination
- Pre-dose vital sign measurement (BP, pulse rate, body temperature)
- PEFR (3 attempts are to be performed, and the best value taken). PEFR should be measured at the same time of day for each visit assessment (eg, morning, afternoon, evening).
- IP administration under observation in the clinic
- Post-dose vital sign measurements (BP, pulse rate) at the following times:
 - Within 15 to 30 minutes post-dose;
 - At 30 minute intervals thereafter, and for the duration of the post-dose observation period is extended beyond 30 minutes.
- Provide subject with take home sachets (or capsules, as appropriate) for daily dosing until next visit
- Monitoring for dosing compliance
- Monitoring for AEs, including allergic symptoms (below and [Section 6.7](#) and [Section 7.2](#))
- Review home dosing instructions (only at first visit in Maintenance Period)

- Subjects will be reminded to continue to follow a peanut-avoidant diet for the duration of the study.

In the event that dose reduction from the stable dose of 300 mg/d is required during the last weeks of the planned 12-week Maintenance Period, the Maintenance Period may be extended on an individual basis up to an additional 4 weeks (to a maximum of 16 weeks) or to a maximum study duration of 56 weeks, whichever is shorter. The Exit DBPCFC must be performed by Study Week 56. Additionally, subjects must maintain a dose of 300 mg/d for at least the last 4 consecutive weeks of the Maintenance Period without the use of symptomatic therapy to qualify for the Exit DBPCFC. Failure to do so will result in the subject being discontinued from the study.

If dosing is discontinued, the subject will be asked to return to the CRC 14 to 16 days following his or her last dose of AR101 to undergo an Early Discontinuation Visit ([Section 6.4](#)).

The procedures for dose reduction and re-escalating back to a dose of 300 mg/d in the Maintenance Period will follow the same guidelines as for the Up-dosing Period.

The procedure for monitoring subjects for safety after in-clinic dosing is the same as for Up-dosing Visits ([Section 6.7.3](#)), except that the initial period of required post-dose observation may be shortened to 30 minutes.

6.3.5 Unscheduled Visits / Unscheduled Blood Draws

The procedures performed at Unscheduled Visits may include spirometry and any or all of those performed at Up-dosing Visits.

Additionally, if a subject or subject's parent/guardian declares his or her intention to discontinue IP dosing, whether at a scheduled visit or an unscheduled visit, a blood draw should be performed for CBC and immunoglobulin assays, and, for subjects who provided prior consent/assent, for optional exploratory immune cell characterization samples. If a blood draw is performed at this time, it will take the place of the Early Discontinuation Visit blood draw.

6.4 Early Discontinuation Visit

Subjects who fail initial escalation or up-dosing, or who prematurely discontinue treatment, will return to the site for an Early Discontinuation Visit. An Early Discontinuation Visit is to occur 14 to 16 days after the last dose of IP.

The following procedures will be performed at the Early Discontinuation Visit:

- Concomitant medication review
- Diet (food allergen) history update
- Completion of the palatability questions
- Completion of the FAQLQ and FAIM questionnaires

- Completion of the TSQM-9 and exit questionnaires
- In subjects with asthma: evaluation of asthma severity using the 2007 NHLBI Criteria ([Appendix 2](#)) and the Asthma Control Test questionnaire
- Complete or symptom-directed physical examination, including weight and height
- Vital signs (BP, pulse rate, body temperature); if DBPCFC is to be conducted, these vital sign measurements should be taken shortly before the first challenge dose
- PEFR, performed in all subjects 6 years of age or older, measured at approximately the same time for each assessment visit. Three attempts of PEFR should be performed, and the best attempt selected. For subjects 4 or 5 years of age: peak flow rates are to be attempted. The attempt must be documented, and a clinical assessment is required. Airflow assessment should be measured at the same time of day as for prior visit assessments (eg, morning, afternoon, evening).
- Spirometry* (FEV₁), performed when PEFR shows a clinically relevant reduction or the subject shows clinical deterioration (eg, active wheeze on physical examination); 3 attempts of FEV₁ should be performed, and the best attempt selected.

*Only for subjects 6 years of age and older who are able to adequately perform spirometry.

- Urine pregnancy test for females of childbearing potential
- Blood draw (same venipuncture for all samples) to collect samples for:
 - Peanut- and peanut component-specific IgE, total IgE, and peanut-specific IgG4 assays
 - CBC
 - Optional blood sample for immune cell characterization assays

The amount of blood to be taken for all tests (required immunoglobulin and CBC and optional immune cell characterization assays) will be included in the manual of procedures and not exceed a total volume of 2.5 mL/kg, to a maximum total of 70 mL on any study day. Blood draw should be collected in compliance with local laboratory guidelines and testing regulations. (For subjects who discontinue early, the blood draw at the Early Discontinuation Visit can be foregone if it was performed at the time that dosing with IP ceased.) Multiple attempts to obtain blood, and repeat samples can be collected where necessary for damaged samples or safety reasons.

- SPT to peanut extract
- Monitoring for AEs, including allergic symptoms ([Section 6.7](#) and [Section 7.2](#))

Study subjects who discontinue the study before the scheduled Exit Visit will remain blinded until the end of the study (final database lock and unblinding), unless emergency unblinding is necessary ([Section 6.12.3](#)).

6.5 Exit Visit

Subjects who tolerate 300 mg/d and are maintained at this dose for approximately 12 weeks (up to a maximum of 16 weeks, see [Section 6.11](#)) will return to the clinic for an Exit Visit.

The following procedures will be performed at the Exit Visit:

- Concomitant medication review
- Diet (food allergen) history update
- Completion of the palatability questions before the Exit DBPCFC
- Completion of the FAQLQ and FAIM questionnaires after the completion of the Exit DBPCFC and unblinding of each subject
- Completion of the TSQM-9 and exit questionnaires after the completion of the Exit DBPCFC and unblinding of each subject
- In subjects with asthma: evaluation of asthma severity using the 2007 NHLBI Criteria ([Appendix 2](#)) and the Asthma Control Test questionnaire
- Complete physical examination, including weight and height
- Vital signs (BP, pulse rate, body temperature) taken shortly before the first DBPCFC dose
- PEFR, performed in all subjects 6 years of age or older, measured at approximately the same time for each assessment visit. Three attempts of PEFR should be performed, and the best attempt selected. For subjects 4 or 5 years of age: peak flow rates are to be attempted. The attempt must be documented, and a clinical assessment is required. Airflow assessment should be measured at the same time of day as for prior visit assessments (eg, morning, afternoon, evening).
- Spirometry* (FEV₁), performed when PEFR shows a clinically relevant reduction or the subject shows clinical deterioration (eg, active wheeze on physical examination); 3 attempts of FEV₁ should be performed, and the best attempt selected.

*Only for subjects 6 years of age and older who are able to adequately perform spirometry.

- Urine pregnancy test for females of childbearing potential
- Blood draw (same venipuncture for all samples), prior to DBPCFC, to collect samples for:
 - Peanut- and peanut component-specific IgE, total IgE, and peanut-specific IgG4 assays
 - CBC
 - Optional blood sample for immune cell characterization assays

The amount of blood to be taken for all tests (required immunoglobulin and CBC and optional immune cell characterization assays) will be included in the manual of procedures and not exceed a total volume of 2.5 mL/kg, to a maximum total of 70 mL

on any study day. Blood draw should be collected in compliance with local laboratory guidelines and testing regulations. Multiple attempts to obtain blood, and repeat samples can be collected where necessary for damaged samples or safety reasons.

- SPT to peanut extract
- Monitoring for AEs, including allergic symptoms ([Section 6.7](#) and [Section 7.2](#))

In addition to the procedures listed above, eligible subjects will have an Exit DBPCFC performed. Eligible subjects are those who tolerate 300 mg/d and are maintained at this dose for the approximately 12-week Maintenance Period. Subjects may have a dose reduction but must be on a dose of 300 mg/d without symptomatic therapy for the 4 weeks immediately preceding the Exit DBPCFC. The Exit DBPCFC is to be conducted in accordance with PRACTALL guidelines, with the protocol-specified modifications, as described in [Section 6.6.2](#).

Each subject participating in the study will be unblinded when he/she completes the Exit Visit procedures (including the Exit DBPCFC for eligible subjects), all major data queries (ie, queries that could influence allocation to 1 or another analysis population) for the subject have been resolved, and the follow-on study ARC008 is available at the study site (refer to [Section 3.3](#)). If the open-label follow-on study ARC008 is not yet available at the study site, the subject may continue blinded study treatment and have clinic visits every 4 weeks in ARC010 until ARC008 is available. Subjects who complete 12 weeks of maintenance and who do not tolerate 300 mg peanut protein at the Exit DBPCFC will not continue blinded study treatment in ARC010.

All AR101-treated subjects who pass the Exit DBPCFC at the 443 mg cumulative dose level of peanut protein (ie, tolerate 443 mg cumulative dose with no more than mild symptoms) are eligible to proceed to ARC008. All placebo-treated subjects who complete the study are eligible for rollover into ARC008.

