3.8.1.2 Other Secondary Efficacy Endpoints

The other secondary efficacy endpoints are as follows:

- The MTD with no more than mild symptoms at Exit DBPCFC
- Change from baseline in MTD of peanut protein at Exit DBPCFC
- Use of epinephrine as a rescue medication at Exit DBPCFC and comparison to its use at Screening DBPCFC
- Changes in serum peanut- and peanut component-specific IgE, total IgE, and peanut-specific IgG4 levels
- Changes in peanut SPT mean wheal diameter
- Quality of life assessments using the food allergy quality of life questionnaire (FAQLQ) and the food allergy independent measure (FAIM; [van der Velde et al, 2010](#)) questionnaire

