6.2 Screening Period

Prior to the commencement of any study-related procedures, the investigator, or designee, must obtain written informed consent/assent from the subject and parent/guardian (as applicable), as described in [Section 11.2](#). The date of signing the consent/assent form is the first day of the Screening Period.

All Screening procedures must be completed no later than 28 days from the signing of the consent/assent form.

Screening will include the following assessments/procedures:

- Informed consent and assent, as age appropriate
- Inclusion/exclusion criteria review
- Review of Subject Eligibility Form
- Medical and allergy history review
- Diet (food allergen exposure) history review
- Concomitant medication review
- Completion of the FAQLQ and FAIM questionnaires anytime during Screening before the DBPCFC

- In subjects with asthma: evaluation of asthma severity using the 2007 NHLBI Criteria ([Appendix 2](#)) and the Asthma Control Test questionnaire
- Complete physical examination, including weight and height
- Vital sign measurement (BP, pulse rate, body temperature). In addition to initial Screening vital sign measurements, vital sign measurements are required just prior to each DBPCFC challenge dose or at 15 to 20-minute intervals post-dose, if the between challenge dosing interval is longer
- Peak expiratory flow rate (PEFR), performed in all subjects 6 years of age or older, measured at approximately the same time for each assessment visit. Three attempts of PEFR should be performed, and the best attempt selected. For subjects 4 or 5 years of age: peak flow rates are to be attempted, but reliable performance is not required for the subject to enter the study or undergo study procedures at the investigating physician's discretion. The attempt must be documented, and a clinical assessment is required.
- Spirometry* (forced expiratory volume in 1 second [FEV₁]), performed when PEFR shows a clinically relevant reduction or the subject shows clinical deterioration (eg, active wheeze on physical examination); 3 attempts of FEV₁ should be performed, and the best attempt selected.

*Only for subjects 6 years of age and older who are able to adequately perform spirometry. In order to assess whether the subject is able to adequately perform spirometry, the spirometry must be attempted, and any attempt must be documented.

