6.12 Study Blinding Procedures

This is a double-blind study. The study as a whole will not be unblinded until after the last subject exits ARC010 and the database is locked.

After undergoing the Exit DBPCFC, most subjects will, however, become de facto unblinded to their on-study treatment assignment on the basis of their experience with the food challenge (ie, subjects who fail 1 part of the Exit DBPCFC early on may reasonably deduce that they had been in the placebo arm of the study), and those who tolerate both parts of the Exit DBPCFC (or fail 1 part only at the highest dose levels tested) may reasonably deduce that they had been in the AR101 arm. Hence, the study is double-blinded on an individual subject basis only up to completion of the Exit DBPCFC. It is for this reason that assessment of reactions to DBPCFC will be made by a Blinded Evaluating Physician (Blinded Assessor).

The risk of bias being introduced into the determination of DLS during DBPCFCs will be substantially reduced by having the assessment of the DBPCFC results made by a Blinded Evaluating Physician (Blinded Assessor) who is not otherwise directly involved, during the treatment phase, with the treatment of the subjects he or she is evaluating.

Additionally, to ensure that allocation of subjects to their appropriate analysis populations is not biased by knowledge of their treatment assignments, specific masking procedures have been put in place to shield study team members who could be involved in determining allocation of the subjects to the analysis populations from knowing subject treatment assignments (refer to Masking Plan). To further ensure that allocation of subjects to their appropriate analysis populations is performed in an unbiased way, subjects will not be informed of their on-study treatment assignments or rollover into the open-label follow-on study until all major data queries (ie, queries that could influence allocation to 1 or another analysis population) have been resolved (as detailed in the Masking Plan).

Subjects who discontinue the study prior to the Exit DBPCFC are not unblinded until after database lock and unblinding of the study as a whole.

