9.2.2.2 Analysis of Other Selected Secondary Endpoints

If all of the key efficacy secondary endpoints are found to be statistically significant, statistical testing of the other secondary efficacy endpoints will continue in the order that they are listed in [Section 3.8.1.2](#) according to the same hierarchical closed testing procedure used for the key efficacy secondary endpoints. The other secondary endpoints are included in the overall hierarchical testing procedure. However, these endpoints are considered supportive in nature to the primary and key secondary endpoints.

Those secondary efficacy endpoints relating to the outcome of the Exit DBPCFC are described below. The statistical methods used for testing the remaining secondary efficacy endpoints are described in the SAP.

- Maximum dose achieved with no or mild symptoms at Exit DBPCFC: The probability estimates for tolerating each challenge dose or higher of the Exit DBPCFC will be calculated based on the discrete hazards model in the ITT population with terms for treatment group effect and the MTD at the Screening DBPCFC (baseline) in the \log_{10} scale ([Chinchilli et al, 2005](#)). Following Chinchilli for the PRACTALL consensus report, the extreme value hazard function will be used for the discrete-time hazard function and the model will be fit with logistic regression with the complementary log-log link function. Subjects with no dose eliciting response at the 1000 mg single dose (2043 mg cumulative) will be censored at that dose. The probability estimates for each dose level will be tabulated by treatment group based on least-squares mean estimates from the above model. The values for MTD for subjects who do not undergo the Exit DBPCFC will be imputed using the maximum doses of peanut protein tolerated in their Screening DBPCFC. The treatment effect hazard ratio and its 95% CI and p-value will be based on the Wald statistic.
- Change from baseline in MTD of peanut protein at DBPCFC: Analyses of change from baseline MTD will be performed using change calculated on the \log_{10} scale. An ANCOVA model of change from baseline MTD at Exit DBPCFC (\log_{10} mg) will be fit with terms for treatment group and the MTD at baseline (\log_{10} mg). The values for MTD for subjects who do not undergo the Exit DBPCFC will be imputed using the MTD of peanut protein in their Screening DBPCFC. The baseline adjusted least-squares means with 95% CIs by treatment group and for the treatment group

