- h) Randomization occurs once subject eligibility has been confirmed by the medical monitor (following the medical monitor's review of the Subject Eligibility Form).
- i) Physical examination including height and weight at: Screening, Initial Escalation Day 1 (not height), and the Up-dosing 80 mg and 300 mg, Exit, and Early Discontinuation Visits. Symptom-directed physical examination (at investigator's discretion [ie, not necessarily include height and weight]) at: Initial Escalation Day 2, Up-dosing Visits (except the 80 mg and 300 mg Up-dosing Visits), and Maintenance Visits.

- j) Vital signs: blood pressure, pulse rate, and body temperature. Screening, Exit, and Early Discontinuation Visits: Where a DBPCFC occurs at these visits, vital signs are measured just before each DBPCFC challenge dose or at 15-20 minutes post-dose, if the between challenge dosing interval is prolonged. Initial Escalation Days 1 and 2: pre-dose and post-dose (within 15-30 minutes post-dose, at 30 minutes thereafter, and for the duration of the post-dose observation period). Up-dosing Visits: pre-dose and post-dose (within 15-30 minutes post-dose, and at 15-30 minute intervals thereafter for the post-dose observation period). Maintenance Visits: As for Up-dosing except post-dose measurements do not need to continue beyond 30 minutes unless the post-dose observation period is extended beyond 30 minutes.
- k) Spirometry (FEV₁) and/or peak expiratory flow rate (PEFR): conducted prior to the start of the DBPCFC, 3 attempts should be made with the best value recorded. PEFR should be measured at the same time of day for each visit assessment (eg, morning, afternoon, evening).
- l) PEFR: 3 attempts should be made with the best value recorded. PEFR should be measured at the same time of day for each visit assessment (eg, morning, afternoon, evening). If a subject's pulmonary status is in question at any time during the study, performance of pulmonary function testing (spirometry) is suggested.
- m) For subjects with asthma only: evaluation of asthma severity using the 2007 NHLBI Criteria ([Appendix 2](#)) and the Asthma Control Test questionnaire.
- n) FAQLQ and FAIM questionnaires to be completed prior to the Screening DBPCFC and after completion of the Exit DBPCFC and the subject's treatment assignment has been unblinded.
- o) TSQM-9 and Exit questionnaire to be completed after completion of the Exit DBPCFC and the subject's treatment assignment has been unblinded.

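### FAQLQ and FAIM at exit are answered after the challenge and after treatment disclosure, yet are tested in the 0.05 hierarchy as if they were blinded outcomes

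*Protocol*

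**What the plan says.** **Timing at exit.** Protocol Section 6.5 lists among the Exit Visit procedures: "Completion of the FAQLQ and FAIM questionnaires after the completion of the Exit DBPCFC and unblinding of each subject". Appendix 1 note n gives the same timing: "after completion of the Exit DBPCFC and the subject's treatment assignment has been unblinded".

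**Timing at baseline.** Section 6.2 asks for "Completion of the FAQLQ and FAIM questionnaires anytime during Screening before the DBPCFC". The baseline answer precedes the challenge and the exit answer follows it.

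**Status of the endpoint.** Section 3.8.1.2 has, as its last item, "Quality of life assessments using the food allergy quality of life questionnaire (FAQLQ) and the food allergy independent measure" (FAIM). It is a secondary efficacy endpoint, separate from the exploratory endpoints in Section 3.8.2.

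**Testing.** Section 9.2.2.2 says that, once the key secondary endpoints succeed, "statistical testing of the other secondary efficacy endpoints will continue in the order that they are listed" in Section 3.8.1.2, under the same closed procedure. It calls these endpoints supportive but keeps them in the overall hierarchy. Section 9.2.2.1 states that the procedure holds the overall Type I error rate at 0.05, two-sided.

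**Extent of the blind.** Section 6.12 accepts that the challenge reveals the arm to most subjects, and concludes that "the study is double-blinded on an individual subject basis only up to completion of the Exit DBPCFC".

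**Order within Section 6.5.** The same section also says "Each subject participating in the study will be unblinded when he/she completes the Exit Visit procedures", once major queries are resolved and ARC008 is available at the site.

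**Early discontinuers.** Under Section 6.4 they complete the same questionnaires at the Early Discontinuation Visit, and "Study subjects who discontinue the study before the scheduled Exit Visit will remain blinded until the end of the study".

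**The concern.** FAQLQ and FAIM are subjective. The protocol does not say who completes them, but at ages 4 to 17 it must be the subject, a parent or both. For everyone who reaches the Exit Visit, the value entering the test is given by someone who knows how the challenge went and which arm the subject was in. The Blinded Assessor described in Section 6.12 protects the reading of the food challenge; it does nothing for a questionnaire.

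A significant result could therefore reflect treatment, knowledge of the arm, knowledge of the challenge result, or a mixture. The plan would still report it as a step in a procedure with 0.05 error control. The SAP is not at hand, but no analysis method can recover a blinded value that was never collected.

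Three smaller points follow from the same timing:

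- **Sequence.** Section 6.5 unblinds a subject on completing the Exit Visit procedures, yet two of those procedures must follow unblinding.
- **Interval.** Because unblinding also waits for query resolution and ARC008, the gap between challenge and questionnaire will vary by subject and site. During that gap some subjects may continue blinded treatment, while those who did not tolerate 300 mg at the Exit challenge do not.
- **Mixing.** If the SAP pools early discontinuers with Exit Visit subjects, blinded and unblinded answers are combined, probably unevenly by arm.

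**Working it through.** **1. Is there any blinded on-treatment value?** The Schedule of Events gives FAQLQ and FAIM at three points only: Screening, Early Discontinuation and Exit. Screening precedes treatment, Early Discontinuation does not apply to Exit Visit subjects, and Exit follows disclosure. For Exit Visit subjects the answer is no.

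**2. The plan's own figure.** No sample size or power is stated for FAQLQ or FAIM. The only figure that governs their test is the two-sided 0.05.

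**3. Inputs for an illustration.**

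- 120 AR101 and 40 placebo subjects (Section 9.4).
- Two-sided 0.05, critical value 1.96 (Section 9.2.2.1).
- Share of AR101 subjects reaching the Exit challenge: 23/29, from ARC001, where 6 of 29 withdrew first and all 26 placebo subjects were completers (Section 1.2.1). Carrying this over to ARC010 is an assumption.
- No true quality-of-life effect, and the test is reached: assumptions.
- Between-arm shift caused by disclosure, d = 0.1, 0.25 or 0.5 SD: an assumption. The documents give no value.

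**4. Formula.** With k = 1/√(1/n₁ + 1/n₂) and noncentrality nc = d·k, the rejection probability is P = P(|Z + nc| > 1.96). At d = 0 this returns 0.05, the plan's figure.

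**5. Results.**

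(a) All 160 compared; 23/29 of AR101 answer after disclosure and the rest answer blinded with no shift. k = 1/√(1/120 + 1/40) = 5.477. The effective shift is d × 23/29 = 0.079, 0.198, 0.397 SD.

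(b) Exit Visit subjects only. 120 × 23/29 ≈ 95 versus 40, so k = 1/√(1/95 + 1/40) = 5.305.

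(c) All 160 answer unblinded, as an upper bound. k = 5.477.

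| Scenario | d = 0.1 | d = 0.25 | d = 0.5 |
|---|---|---|---|
| (a) nc | 0.434 | 1.086 | 2.172 |
| (a) false-positive rate | 0.072 | 0.192 | 0.584 |
| (b) nc | 0.531 | 1.326 | 2.653 |
| (b) false-positive rate | 0.083 | 0.264 | 0.756 |
| (c) nc | 0.548 | 1.369 | 2.739 |
| (c) false-positive rate | 0.085 | 0.278 | 0.782 |

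Scenario (a) places the whole shift in the AR101 arm. If part of it is a change in placebo answers, that part is not diluted, since all placebo subjects are taken to reach the Exit Visit; the rate then lies between (a) and (c).

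**6. Reach.** The endpoint is the last item in the last tested list. Nothing is tested after it, so no earlier test is affected.

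**The case against.** **Learning the result may be part of the benefit.** Section 1.1 locates much of the quality-of-life burden in fear of accidental exposure, and Section 1.4 treats telling subjects they are desensitized as important. The placement may be deliberate, since palatability is asked before the challenge and FAQLQ/FAIM after it. This stands in part: some of any shift is arguably a consequence of treatment rather than error. It is a reason to keep a post-challenge assessment. It does not justify waiting for formal disclosure, or presenting the answer as an error-controlled blinded comparison.

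**The magnitude is hypothetical.** It is: no document supports any particular shift, and its direction could vary, since placebo completers learn that they may enter ARC008 while AR101 subjects who fail at 443 mg cumulative learn that they may not. The rates also apply only if every earlier test succeeds, and a complete absence of quality-of-life effect would then be a demanding null. The figures show sensitivity and are not a forecast.

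**Earlier timing does not guarantee a blind.** In ARC001, treatment-emergent hypersensitivity events occurred in 90% of AR101 and 50% of placebo subjects (Section 1.2.1), so some will guess their arm before the challenge. That is true. The change reduces the bias without assuring its removal.

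**Pooling depends on an unseen SAP, and the sequence conflict is editorial.** Both are fair. Sections 3.3 and 4.3.1 and Appendix 1 note bb tie unblinding to the Exit DBPCFC, which gives a workable order. Neither point carries the conclusion.

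**The endpoint is supportive and last.** This limits the severity, but the protocol still tests it under the 0.05 claim.

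**Conclusion.** The concern holds. As written, the plan produces a formally tested comparison of subjective reports collected after both the challenge and treatment disclosure, with no blinded alternative for Exit Visit subjects. A significant FAQLQ or FAIM result could not be read as a blinded treatment effect.

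The size cannot be derived from the documents. Under the assumptions shown, a small disclosure shift of 0.1 SD moves the false-positive rate from 5% to about 7–8.5%; 0.25 SD moves it to 19–28%, and 0.5 SD to 58–78%. Any nonzero shift takes the test above its stated level.

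The consequence is confined to one supportive, last-ranked endpoint. The point should be fixed because the remedy is simple, but it does not threaten the trial's main conclusions.

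**What to change.** - **Timing.** In Section 6.5 and Appendix 1 note n, have FAQLQ and FAIM completed before the first part of the Exit DBPCFC, alongside the palatability questions, matching the order at Screening. Moving them to after the challenge but before disclosure would not be enough, because Section 6.12 accepts that the challenge itself reveals the arm to most subjects.
- **Testing.** Use the pre-challenge value for the hierarchical test.
- **Second assessment.** Keep the post-unblinding completion as a descriptive, open-label measure, so that the effect of learning the result is still recorded.
- **Sequence.** Reword the unblinding sentence in Section 6.5 so that disclosure does not wait on procedures that must follow it.
- **Fallback.** If the timing cannot change, remove FAQLQ and FAIM from the alpha-controlled chain and report them as open-label. Being last, their removal costs no other endpoint anything.

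The cost is wording in two places and one extra questionnaire completion at a visit where blood draws and palatability questions already precede the challenge. The downside is that the tested value will not capture reassurance from passing the challenge; the retained second assessment would. The protocol does not state whether subjects have already exited. If some have, changing the timing would create two assessment schedules, and the fallback is cleaner.
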